4. OBJECTIVES

4.1 Primary objective

The study proposes the evaluation of the side effects of the proposed experimental radiotherapy treatment and the acceptability of the risk / benefit ratio.

Acute / subacute toxicity will be analysed with recording of adverse events (related or unrelated) reported during the entire treatment and within 3 months of its end.

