6.7 Changes or suspension of treatment

During the treatment program, neurological toxicities will be evaluated according to criteria of the National Cancer Institute Common Toxicity Criteria for Adverse Events (NCI CTCAE), version 4.0. The patient will be monitored for the appearance of adverse events for the entire duration of the study, including the follow-up period.

Events	Actions
a) Neurological toxicity \leq grade 2 responsive to supportive care b) Grade \leq 3 non-neurological toxicity	The RadioTherapy treatment continue
c) grade $>$ 3 neurological and non-neurological toxicity; d) grade \leq 2 neurological toxicity unresponsive to supportive care; e) disease progression during treatment; f) second medical opinion, for safety reasons; g) refusal of the patient to continue the treatment; h) need to start antineoplastic therapy.	The presence of at least one of the events determines the definitive suspension of the treatment. It also involves leaving the study in cases (e) and (h)

In case of grade \leq 2 neurological toxicity with response to adequate supportive therapy (steroids, mannitol, anticomitials) the radiotherapy treatment will continue.

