8.3 Follow-up evaluation

Clinical visits at 7 days, 15 days, 30 days, 60 days and 90 days from the end of radiotherapy (RT).

8.3.1 Mandatory assessments:

- General and neurological examination. A palliative doctor will be supported by the radiotherapist.
- Detection of vital parameters and anthropometric indices.
- Definition of the ECOG and Karnofsky indices.
- Detection of acute / subacute / late toxicity by CTCAE version 4.0 scale.
- Quality of life assessment through EORTC QLQ-C30 and BN20 questionnaires (at 1 and 3 months).
- MRI of the brain before and after m.d.c. paramagnetic (1 month and 3 months from the end of RT).

8.3.2 Optional assessments based on tumor site or patient's particular condition:

- Additional specialist visits (endocrinology, ophthalmology, etc.) according to medical indications.

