9. OUTCOMES EVALUATION PLAN

The response to radiotherapy treatment will be evaluated according to the RANO criteria (Technical Annex) with morphological and functional (multiparametric) brain MRI performed at 1 month after the end of radiotherapy and then after 3 months.

The toxicity assessment will be made with reference to the International Common Toxicity Criteria for Adverse Event (CTCAE) - version 4.0 (The complete document is available on the website of the National Institute of Health

The response to radiotherapy treatment will be evaluated according to the RANO criteria (Annex) with morphological and functional (multiparametric) brain MRI performed at 1 month after the end of radiotherapy and after 3 months.

The toxicity assessment will be made with reference to the International Common Toxicity Criteria for Adverse Event (CTCAE) - version 4.0 (The complete document is available on the National Institute of Health (NIH) website at the following address: <http://ctep.cancer.gov/reporting/ctc.html>), excluding neurological adverse events of grade ≤ 2 that responded adequately to supportive care.

Safety and tolerability will be defined for:

- type, frequency, severity and relationship of adverse events to treatment;
- number of subjects who prematurely discontinued treatment due to any adverse event;
- frequency of clinically significant changes and / or laboratory tests.

All patients who have started radiation treatment will be considered for analysis, until the completion of the study (i.e. until the final visit at the end of the entire program for patients who complete the treatment) or until the scheduled follow-up visit in case of premature suspension of the study. Patients will be instructed by the Investigator on the need to report any adverse events that may occur during the study.

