10.2 Recording an Adverse Event

The Investigator must record any adverse events that occur during the treatment period and thereafter, up to the study closing visit in the CRF and in the relevant health records.

A completely resolved AE that recurs or increases in severity will have to be recorded as a new event within the CRF.

A description of the event will be reported with medical terms, date of presentation and resolution, severity, causation with respect to the treatment, actions taken, seriousness of the event. All the measures required for the management of the adverse event must be recorded in the reference health documentation.

If an AE is considered serious, the AE section within the CRF must be completed.

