12. STATISTICAL ASPECTS

12.1 The champion

The study is proposed as an exploratory, prospective, experimental and monocentric study.

Regarding the main endpoint (toxicity of the proposed radiotherapy treatment), there are no data currently available from previous studies. In the absence of criteria useful for the sizing of the

sample in formal terms, the sample (12 cases) is defined according to criteria of opportunity and feasibility, with two steps of evaluation of the outcome as follows:

- after the first 3 patients enrolled and treated with the proposed radiotherapy scheme, there will be a 1 month stop in the enrollment of subsequent patients, in which tolerance and the occurrence of serious adverse events will be analyzed.
- At the end of the month, if none of the patients treated shows toxicity attributable to radiation treatment > 3, the enrollment of the next 3 patients will continue with a further stop in enrollment for another month.
- If these patients, together with the 3 previously treated, do not have serious adverse events induced by radiation treatment, the enrollment of the last 6 patients will continue.

All patients in the study will be followed, for the primary endpoint of the study, for at least 3 months from enrollment, or until disease progression or death from another cause.

At the end of each intermediate step, the investigator will produce a report on the safety of the cases already treated which will be subjected to the evaluation of an internal board, composed of the Health Director, the Scientific Director and the Legal Doctor of the ASMN-IRCCS of Reggio Emilia, who will express on the continuation / interruption of the study and subsequently notified to the EC.

The internal board will also evaluate any urgent safety measures (as defined in paragraph 11.4) transmitted by the RAV, expressing its opinion on the continuation / interruption of the study and subsequently notifying the EC of this opinion.

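### Section 12.1 lets follow-up for the primary toxicity endpoint stop at disease progression, while 4.1 and 8.3 run it to 3 months after radiotherapy; following 12.1 can only lower the reported toxicity or leave it unchanged

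*Combined protocol and SAP*

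**What the plan says.** Section 12.1 sets a follow-up rule expressly for the primary endpoint: "for at least 3 months from enrollment, or until disease progression or death from another cause".

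Other sections describe a longer observation period:

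- Section 4.1 defines the endpoint through "recording of adverse events (related or unrelated) reported during the entire treatment and within 3 months of its end".
- Section 8.3 schedules clinical visits with CTCAE grading at 7, 15, 30, 60 and 90 days after the end of radiotherapy, with no exception for patients who have progressed.
- Section 6.7 states: "The patient will be monitored for the appearance of adverse events for the entire duration of the study, including the follow-up period".
- Section 9 says of the analysis set: "All patients who have started radiation treatment will be considered for analysis, until the completion of the study". It explains completion as "until the final visit at the end of the entire program for patients who complete the treatment".
- Section 10.2 has adverse events recorded "up to the study closing visit".

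Two places lean the other way. The table in 6.7 has patients leave the study on progression during treatment (case e) or on needing antineoplastic therapy (case h). Section 13.3, on early termination of treatment, can be read as ending monitoring at documented progression, though its wording is unclear.

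On the denominator, section 9 includes everyone who started radiotherapy, and 7.2 keeps patients whose treatment was stopped for progression in the endpoint analysis. Section 12.2 plans percentages with Clopper-Pearson intervals.

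**The concern.** Section 12.1 is the only follow-up rule that names the primary endpoint, and it stands in the statistical chapter, so a site or analyst could reasonably follow it. A patient who progresses before day 90 would then stay in the denominator with part of the toxicity window unobserved, and would count as event-free unless an event had already occurred.

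Early progression is common in this disease, so more than an occasional patient could be affected. Safety is the primary objective because, according to section 2, no study gives clear indications on toxicity in brain tissue that has already been irradiated. Data not collected after progression cannot be restored by any choice of analysis.

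**Working it through.** **No plan figure to reproduce.** The sample of 12 (3 + 3 + 6) is set by feasibility, without a formula, assumed toxicity rate or power. The check covers the direction and size of the effect.

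**Direction.** The denominator is fixed (sections 9 and 7.2) and the numerator counts patients with an event. Shortening observation removes events and never adds them, so the percentage falls or stays the same. In 20,000 simulated trials of 12 patients (25% risk, onset uniform over 3 months, median PFS 5 months, immediate stop at progression) the count rose in none and fell in 44%. If progressing patients were instead dropped from the denominator, the percentage rose in 67% of trials, but the documents do not plan that.

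**Inputs for size.**

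- Median PFS *m*: Table 1 gives 23 median PFS values, from 2.6 to 10.5 months, with median 5.0 (mixed histologies and drug combinations). In one row GBM and HGG figures follow the PFS value; I read those as survival and count only the 4.9.
- Assumed: exponential PFS from the end of radiotherapy, S(t) = 2^(−t/m), t in months.
- Assumed: true 90-day risk 25%, independent of progression. The documents give no rate.
- Assumed: all collection stops when progression is detected, and patients cut short without an event count as event-free.
- Detection: (A) at the 1- and 3-month MRIs only; (B) at the next scheduled visit; (C) at once.

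**Patients of 12 cut short.** A: 12·(1 − S(1)); B: 12·(1 − S(2)); C: 12·(1 − S(3)). At m = 5, S(1) = 0.871, S(2) = 0.758 and S(3) = 0.660.

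| m (months) | A | B | C |
|---|---|---|---|
| 2.6 | 2.81 | 4.96 | 6.61 |
| 5.0 | 1.55 | 2.91 | 4.08 |
| 10.5 | 0.77 | 1.48 | 2.16 |

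**Reported rate.** On a detection grid: Σ[S(t_prev) − S(t)]·F(t) + S(3)·F(3), with grid {1, 3} for A and {7/30, 0.5, 1, 2, 3} for B. For C: ∫₀³ λe^(−λt)F(t)dt + S(3)·F(3), with λ = ln2/m. Three onset patterns F(t) are used:

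- all onset in month 1: 0.25·min(t, 1);
- constant hazard: 1 − 0.75^(t/3);
- onset over months 1 to 3: 0.25·(t − 1)/2 after month 1, and 0 before.

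Example (m = 5, A, months 1 to 3): F(1) = 0 and F(3) = 0.25, so the rate is 0.871 × 0.25 = 21.8%.

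| m | Onset | A | B | C |
|---|---|---|---|---|
| 2.6 | month 1 | 25.0% | 23.0% | 21.9% |
| 2.6 | constant | 21.3% | 19.2% | 17.5% |
| 2.6 | months 1–3 | 19.1% | 16.9% | 14.8% |
| 5.0 | month 1 | 25.0% | 24.0% | 23.3% |
| 5.0 | constant | 22.9% | 21.7% | 20.7% |
| 5.0 | months 1–3 | 21.8% | 20.4% | 19.0% |
| 10.5 | month 1 | 25.0% | 24.5% | 24.2% |
| 10.5 | constant | 24.0% | 23.4% | 22.8% |
| 10.5 | months 1–3 | 23.4% | 22.7% | 21.9% |

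The largest shortfall, 12 × (25% − reported rate) before rounding, is 1.22 patients at m = 2.6, 0.72 at m = 5 and 0.37 at m = 10.5. At m = 5 the largest shortfall is 0.29 for a true risk of 10% and 1.15 for 40%.

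**Benchmark.** Clopper-Pearson 95% interval for 3/12: 5.5% to 57.2%.

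**Progression during the 5 sessions** (6.7, case e): taking 5 days at the same hazard and m = 5, 12·(1 − S(5/30.4)) = 0.27 patients. The exposure therefore lies almost wholly in patients who have finished radiotherapy.

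**The case against.** Most of the protocol already points to full collection. Section 12.1 is one sentence that sets a minimum and does not forbid continuing, so the loss occurs only if staff let it override the objective, the visit schedule and the recording rules. That is fair, and it makes the bias conditional. But the minimum attaches to the 3 months; the progression branch still permits an earlier stop, and nothing tells staff which text governs.

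Section 10.1.3 has events followed to resolution or stabilization, possibly beyond study end. This protects events already open at progression. The loss concerns new events only, and the calculation counts only those.

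Section 5.1 lists, without a clear and/or, what makes treatment completed, including the first follow-up MRI. A patient who progresses before that MRI (up to 1.55 of 12 at m = 5) is therefore not clearly a completer under section 9. This weakens the support from section 9 for those patients; 4.1, 8.3, 6.7 and 10.2 do not depend on it.

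Attribution is harder after progression or new therapy, and 12.1 describes its endpoint as toxicity of the radiotherapy. So the understatement of treatment-related toxicity alone may differ from the figures above. Attribution still does not justify a stop: 4.1 records unrelated events too, and 10.1.2 has the investigator judge causality.

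The effect is also small in a 12-patient descriptive study without a hypothesis test. With detection by MRI only, at m = 5 and 25% risk, it is 0 to 0.39 of a patient. The one-month continuation steps are affected less than the final result.

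**Conclusion.** The concern holds. Section 12.1 conflicts with 4.1 and 8.3 on when observation for the primary endpoint may end, and no order of precedence is given. With the planned denominator, following 12.1 lowers the crude toxicity percentage or leaves it unchanged, whatever the assumed risk or PFS.

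The size does rest on the assumptions: exponential PFS in the Table 1 range, a 25% risk independent of progression, and complete cessation of collection. At median 5 months a true 25% would be reported as 19% to 25%, at most 0.7 of a patient in 12. Over the whole Table 1 range the lowest figure is 14.8%, about 1.2 patients. Sampling uncertainty is far larger, but it is shown by the interval, whereas this shortfall is not.

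Section 12.1 also counts from enrollment and 4.1 from the end of treatment. Because 12.1 gives a minimum, that is only a wording mismatch. Overall this should be fixed, though it does not undermine the study.

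**What to change.** Reword 12.1 to agree with 4.1 and 8.3, for example:

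> For the primary endpoint, toxicity data are collected for all patients who start radiotherapy until 90 days after the last fraction, death or withdrawal of consent, whichever comes first, irrespective of disease progression or new antineoplastic therapy.

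Reconcile 13.3 and the study-exit wording in 6.7 (cases e and h) with this for data collection only; the treatment-suspension rules are untouched. Record the dates of progression and of any new antineoplastic therapy, so that later events can be identified in the listings.

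The cost is a short wording amendment. Visits to day 90 are already scheduled, and overall survival already needs contact after progression. The drawback is harder attribution of events after progression or new therapy; the recorded dates and the causality assessment in 10.1.2 make those events visible to the reader.

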12.2 Analysis plan

By virtue of the exploratory nature of the study and the limited number of subjects, the data will be presented mainly through tables and lists. Confidence intervals for percentages will be calculated following the Clopper-Pearson method to properly take into account the limited number of subjects. OS and PFS will be graphed using the Kaplan-Meier method and briefly described in percentile terms. The analyses will be conducted with R, SAS System, or SPSS software on the basis of availability at the time of the analyzes and in the versions in use in that period

12.3 Data management

For the management of the study, a data collection form on the web platform (e-CRF) with personalized access credentials will be requested from the Company's IT Service (STIT), which meets regulatory requirements and guarantees privacy criteria in accordance with the law (Authorization of the Privacy Guarantor n.72 of 26 March 2012). All data will be collected and processed in codified form.

A paper draft of the CRF will be provided to the Ethics Committee, which is being prepared.

Patients will be registered in the CRF, registration form, at the time of entry into the study (Signature of informed consent). All signed consents and patient screening and enrolment procedures must be kept in the study's Trial Master File.

13. ETHICAL AND AUTHORIZATION ASPECTS

13.1 General aspects

The study will be activated only after approval by the Local Ethics Committee / competent Authorities, and any communications to the Ministry of Health and will be conducted in accordance with this protocol and any amendments introduced.

The protocol has been written and the study will be conducted in accordance with the ethical principles of the Declaration of Helsinki (<http://www.wma.net/e/policy/b3.htm>) and ICH Harmonized Tripartite Guideline for Good Clinical Practice (<http://www.ifpma.org/pdfifpma/e6.pdf>) and UNI ISO 14155 (2012) (Clinical investigation of medical devices for human subject-GCP) and following the guidelines on the medical device vigilance system Meddev 2.12-1.

The study documentation will be collected and stored at the participating centers and in its entirety by the coordinating center of the study (Medical Physics Service, ASMN-IRCCS of Reggio Emilia) and will be stored according to regulatory indications.

All documentation must be made available for any inspections required by regulatory authorities, during or after the conclusion of the study, and for planned monitoring activities.

Each patient eligible for treatment will be adequately informed by the specialist on the purposes of the study, the expectations of the proposed experimental intervention, the objectives and methods of conducting the study and must sign a specific consent for the study and data processing.

Each patient has the right to withdraw their membership at any time without having to justify the choice; from that moment on his data will no longer contribute to the study dataset and documented in the patient's medical record.

13.2 Insurance aspects

The study in question is defined as a non-profit study, aimed at improving clinical practice as an integral part of health care; no medicine is envisaged and the study has no industrial purpose. In these cases, the legislation decrees that as a guarantee for any damage caused to the patient to cover the risks associated with the experimental treatment not already documented, it is possible to take advantage of the coverage already provided for the assistance activity which is also extended to the experimentation activities.

The information on the risks known to the treatment and on the company insurance policy covering the study must be specifically provided to the patient in the information documentation, before signing the consent.

13.3 Monitoring and Quality Control (QC)

Through an electronic e-CRF set up on a web platform by the IT Service of the ASMN-IRCCS company, of Reggio Emilia (promoter of the study), the registration of patients entering the study and the availability of clinical data will be guaranteed with continuity.

The Clinical Studies and Statistics Office will propose a monitoring program suitable for the type of study in accordance with the company SOPs with centralized monitoring actions, off site and on site, managed by adequately trained staff.

In the event of early termination of treatment, patients will still be monitored for the entire duration of the study or for any documented disease progression, death or exit from follow-up.

13.4 Responsibility and publication policy

The study is independent and promoted by the IRCCS-ASMN Hospital which will manage the conduct of the study, the collection and analysis of data and its dissemination.

The submission of articles to scientific journals and / or the presentation of papers at national / international scientific conferences will be attended by the experimenters interested in the study and those who participated in the development and drafting of the project.

The results will be published and / or presented at scientific conferences even in the event of an early interruption of the study.

